7.2. Secondary Pharmacokinetic Analyses

7.2.1. Endpoint / Variables

7.2.1.1. Drug Concentration Measures

Refer to Appendix 3: Data Display Standards & Handling Conventions (Section 11.3.3 Reporting Standards for Pharmacokinetic).

7.2.1.2. Derived Pharmacokinetic Parameters

Pharmacokinetic parameters will be calculated by standard non-compartmental analysis according to current working practices and using the currently supported version of WinNonlin (8.0 or higher). All calculations of non-compartmental parameters will be based on actual sampling times. Participants who experience emesis at or before 2 times median Tmax or participants whose pre-dose concentrations are >5% of their Cmax value for the given treatment will be excluded from the calculation of summary statistics for the respective treatment.

Plasma PK parameters listed below will be determined from the plasma concentration-time data, as data permits:

Parameter	Parameter Description
Tmax	Time of maximum observed concentration
Tlag	Lag time for absorption
t1/2	Apparent terminal phase half-life
CL/F	Apparent clearance following extravascular administration

NOTES:

- Additional parameters may be included as required.

7.2.2. Summary Measure

Pharmacokinetic parameters Tmax, Tlag, t1/2, and CL/F following single dose administration of GSK3640254 and DTG administered together as single agents and following single dose administration of FDC tablet formulations of GSK3640254 / DTG to healthy participants.

7.2.3. Population of Interest

The secondary PK analyses will be based on the PK parameter population for plasma PK parameters, unless otherwise specified.

7.2.4. Statistical Analyses / Methods

Details of the planned displays are provided in Appendix 9: List of Data Displays and statistical principles.

Unless otherwise specified, endpoints/variables defined in Section 7.2.1 will be summarized using descriptive statistics and listed.

Secondary plasma PK parameters Tmax, Tlag, t1/2, and CL/F will be estimated for GSK3640254 and DTG. Summary statistics (arithmetic mean, geometric mean, median, CV, SD, minimum, maximum, CVb, and 95% CI) for secondary plasma PK parameters of GSK3640254 and DTG will be summarized by treatment.

8. SAFETY ANALYSES

The safety analyses will be based on the Safety population, unless otherwise specified.

8.1. Adverse Events Analyses

Adverse events (AEs) analyses including the analysis of AEs, serious (SAEs), and other significant AEs will be based on VH/GSK's Integrated Data Standards Library standards. The details of the planned displays are provided in Appendix 9: List of Data Displays.

Adverse events will be assigned to the last treatment received prior to start date/time of the AE. If no time was reported for an AE and the date is the same as date of dosing, the AE will be assigned to the treatment dosed on that day. Adverse events occurring after the last dose date and time + 5 days (Day 6 and beyond for each treatment period) and before the dose date and time of the next treatment will not be summarized but will be listed.

8.2. Clinical Laboratory Analyses

Laboratory evaluations including the analyses of chemistry laboratory tests, hematology laboratory tests, urinalysis, pregnancy tests, and other screening tests will be based on VH/GSK's Integrated Data Standards Library standards and will be graded using the Division of AIDS (DAIDS) Table for Grading the Severity of Adult and Pediatric Adverse Events (Version 2.1, July 2017). The details of the planned displays are in Appendix 9: List of Data Displays.

8.3. Adverse Events of Special Interest

-At the end of the study, QT prolongation, gastrointestinal intolerance, gastric toxicity, psychiatric events, nervous system disorders, and skin and subcutaneous tissue disorders will be summarized by treatment. A listing will also be provided accordingly.

The AESI of QT prolongation will be defined as cardiac disorders system organ class (SOC) plus preferred terms (PTs) using the Medical Dictionary for Regulatory Activities (MedDRA) Standardized MedDRA Query (SMQ) "Torsade de pointes/QT Prolongation" (narrow and broad terms) plus seizure.

Gastrointestinal intolerance and gastric toxicity AESIs will be defined within three narrow sub-SMQs [Gastrointestinal nonspecific symptoms and therapeutic procedures SMQ; Gastrointestinal nonspecific dysfunction SMQ; Gastrointestinal nonspecific inflammation (SMQ)] plus a selection of relevant broad PTs from the Gastrointestinal non-specific symptoms and therapeutic procedures SMQ.

Psychiatric AESI will be defined within the following:

- Sub-SMQ "Suicide/self-injury" (SMQ) from parent SMQ of "Depression and Suicide/Self Injury". Only narrow terms from the sub-SMQ will be selected.

- Sub-SMQ “Depression (excluding suicide and self-injury)” (SMQ) from parent SMQ of “Depression and Suicide/Self Injury”. Only narrow terms from the sub-SMQ will be selected.
- All PTs from high level group term (HLGT) “Manic and Bipolar Mood Disorders and Disturbances” under SOC “Psychiatric Disorders”.
- Narrow terms from SMQ “Psychosis and Psychotic Disorders” selected.
- All PTs from HLG “Anxiety Disorders and Symptoms”, under SOC “Psychiatric disorders”.
- All PTs from HLG “Sleep Disorders and Disturbances” and HLG “Sleep disturbances (include subtypes)”.

Nervous system disorders AESIs will be defined within the following:

- Four HLGs under Nervous System Disorders SOC: “Headaches”; “Mental impairment disorders (excluding dementia)”; “Disturbance in consciousness” and “Seizures and seizure disorder”

Skin and subcutaneous tissue disorder AESIs will be defined with the following PTs:

Skin and subcutaneous tissue disorders term to be provided when the final analysis is carried out(term will include rash, maculopapular rash, urticaria etc).

8.4. Other Safety Analyses

The analyses of non-laboratory safety test results including ECGs, vital signs, pregnancy, and Columbia-Suicide Severity Rating Scale (CSSR-S) questionnaire will be based on VH/GSK’s Integrated Data Standards Library standards, unless otherwise specified. A figure of mean change from baseline in QTc using the Fridericia formula (QTcF) interval along with the 2-sided 95% CI using Student’s t distribution will be presented by treatment and visit. The details of the planned displays are presented in Appendix 9: List of Data Displays.

9. ADDITIONAL ANALYSES DUE TO THE COVID-19 PANDEMIC

9.1. Study Population

9.1.1. Additional Displays for Participants with a COVID-19 Infection

A participant is defined as having a suspected, probable, or confirmed COVID-19 infection during the study if the answer is “Confirmed”, “Probable”, or “Suspected” to the case diagnosis question from the COVID-19 coronavirus infection assessment eCRF.

Summaries and listings of the numbers of participants with a suspected, probable, or confirmed COVID-19 infection, and of COVID-19 test results will be based on VH/GSK’s Integrated Data Standards Library standards. The details of the planned displays are provided in Appendix 9: List of Data Displays.

9.2. Safety

9.2.1. Assessment of COVID-19 AEs

A Standardised MedDRA Query (SMQ) will be used to identify all COVID-19 AEs.

The incidence of AEs and SAEs (Fatal and Non-Fatal) of COVID-19, COVID-19 AEs leading to study drug discontinuation, COVID-19 AEs leading to study withdrawal, and COVID-19 AEs by severity, will be obtained from standard AE and SAE summaries.

11. APPENDICES

11.1. Appendix 1: Schedule of Activities

11.1.1. Protocol Defined Schedule of Events

Screening Visit (Part 1 and Part 2)

Visit Window (relative to Day 1)	Screening (up to 35 days before Day 1)
Outpatient Visit	X
Informed Consent	X
Inclusion and exclusion criteria	X
Demography	X
Full physical examination including height and weight ¹	X
Laboratory assessments (hematology, clinical chemistry, urinalysis)	X
12-lead electrocardiogram	X
Vital sign measurements	X
Medication/drug/alcohol history	X
Past and current medical conditions	X
Columbia-Suicide Severity Rating Scale	X
Serum pregnancy test	X
Follicle-stimulating hormone (as needed, to confirm postmenopausal status)	X
Drug, alcohol, and cotinine screen	X
Human immunodeficiency virus, hepatitis B and C screening	X
Molecular test for SARS-CoV-2 ²	X
1. A full physical examination will include at a minimum, assessments of the skin, cardiovascular, respiratory, gastrointestinal, and neurological systems.	
2. Two consecutive approved molecular tests (polymerase chain reaction or antigen test). The first test should be performed ≥ 7 days prior to admission.	

Time and Events (Part 1)

Procedure	Check-in	Baseline ¹	Period 1 & 2			Period 3				Notes	
	Day -2	Day -1	Day 1	Washout			Day 1	Day 2	Days 3-4	Day 5 ²	
				Day 2	Days 3-5	Days 6-7					
Admit to clinic	X										
Discharge from clinic										X	Discharge from clinic following completion of the last study procedure on Day 5 of Period 3.
Brief physical examination		X				D7				X	Interim or symptom-targeted physical examination will be performed at the discretion of the investigator. See Section 8.2.1 of the protocol for description of brief physical examination.
Vital signs		X	X	X	D3	D7	X	X	X	X	Blood pressure and pulse will be measured in triplicate at predose on Day 1 in all periods. Single blood pressure and pulse will be measured on other study days.
Temperature check	X	X	X	X	X	X	X	X	X	X	
12-lead ECG		X	X				X			X	The ECGs on Day 1 in all periods will be taken at predose, and post-dose at 2, 4, and 6 hours. The predose ECGs will be taken in triplicate to establish a baseline QTcF. The post-dose ECGs are single ECGs.
Drug, alcohol, and cotinine screen	X										See Appendix 2 of the protocol for specific tests to be performed.
Molecular test for SARS-CoV-2	X*				D5					X	* The second test will be performed on Day -2 after admission to the clinic. Participants will be quarantined within the clinic until the second test result is negative. Once the second test result is confirmed negative, participants can be released into the study unit and will follow infection control practices.
Laboratory assessments (hematology, chemistry, urinalysis)		X ³		X		D7		X		X	See Appendix 2 of the protocol for specific tests to be performed. Day 2 samples in each period to be collected 24 hours after dosing.
Pregnancy test	X									X	Serum testing on Day -2
Columbia-Suicide Severity Rating Scale		X				D7				X	
Study intervention: GSK3640254 25 mg, 100 mg or GSK3640254 / DTG 150 mg / 50 mg fixed-dose combination Or DTG 50 mg			X				X				See Section 4.1. of the protocol
GSK3640254 PK sampling			X	X	D3, D4, D5		X	X	X	X	Blood for PK analysis of GSK3640254 will be collected within 40 minutes prior to dosing and 0.5, 1, 1.5, 2, 2.5, 3, 3.5, 4, 4.5, 5, 6, 8, 12, 24, 48, 72, and 96 hours post-dose in all periods.

CONFIDENTIAL

213055

Procedure	Check-in	Baseline ¹	Period 1 & 2			Period 3				Notes	
	Day -2	Day -1	Day 1	Washout			Day 1	Day 2	Days 3-4	Day 5 ²	
				Day 2	Days 3-5	Days 6-7					
Dolutegravir PK sampling			X	X	D3, D4, D5		X	X	X	X	Blood for PK analysis of dolutegravir will be collected within 40 minutes prior to dosing and 0.5, 1, 1.5, 2, 2.5, 3, 3.5, 4, 4.5, 5, 6, 8, 12, 24, 48, 72, and 96 hours post-dose in all periods.
AE review	←=====X=====→										
SAE review	←=====X=====→										
Concomitant medications	←=====X=====→										

AE = adverse event; D = day; ECG = electrocardiogram; PK = pharmacokinetic; QTcF = QT interval corrected using Fridericia's formula; SAE = serious adverse event.

1 Baseline assessments will be collected on Day -1 before Period 1.

2 Evaluations scheduled for Day 5 in Period 3 will also be performed for participants who discontinue early.

3 Review and approval prior to dosing on Day 1 in Periods 1, 2 and 3..

Time and Events (Part 2)

Procedure	Check-in	Baseline ¹	Period 1			Period 2				Notes	
	Day -2	Day -1	Day 1	Washout			Day 1	Day 2	Days 3-4	Day 5 ²	
				Day 2	Days 3-5	Days 6-7					
Admit to clinic	X										
Discharge from clinic										X	Discharge from clinic following completion of the last study procedure on Day 5 of Period 2.
Brief physical examination		X				D7				X	Interim or symptom-targeted physical examination will be performed at the discretion of the investigator. See Section 8.2.1 of the protocol for description of brief physical examination.
Vital signs		X	X	X	D3	D7	X	X	X	X	Blood pressure and pulse will be measured in triplicate at predose on Day 1 in both periods. Single blood pressure and pulse will be measured on other study days.
Temperature check	X	X	X	X	X	X	X	X	X	X	
12-lead ECG		X	X			D7	X			X	The ECGs on Day 1 in all periods will be taken at predose, and post-dose at 2, 4, and 6 hours. The predose ECGs will be taken in triplicate to establish a baseline QTcF. The post-dose ECGs are single ECGs.
Drug, alcohol, and cotinine screen	X										See Appendix 2 of the protocol for specific tests to be performed.
Molecular test for SARS-CoV-2	X*				D5					X	* The second test will be performed on Day -2 after admission to the clinic. Participants will be quarantined within the clinic until the second test result is negative. Once the second test result is confirmed negative, participants can be released into the study unit and will follow infection control practices.
Laboratory assessments (hematology, chemistry, urinalysis)		X ³		X		D7		X		X	See Appendix 2 of the protocol for specific tests to be performed. Day 2 samples in each period to be collected 24 hours after dosing.
Pregnancy test	X									X	Serum testing on Day -2
Columbia-Suicide Severity Rating Scale		X				D7				X	
Study intervention: GSK3640254 25 mg, 100 mg or GSK3640254 / DTG 150 mg / 50 mg fixed-dose combination Or DTG 50 mg			X				X				See Section 4.1. of the protocol

Procedure	Check-in	Baseline ¹	Period 1			Period 2				Notes	
	Day -2	Day -1	Day 1	Washout			Day 1	Day 2	Days 3-4	Day 5 ²	
				Day 2	Days 3-5	Days 6-7					
GSK3640254 PK sampling			X	X	D3, D4, D5		X	X	X	X	Blood for PK analysis of GSK3640254 will be collected within 40 minutes prior to dosing and 0.5, 1, 1.5, 2, 2.5, 3, 3.5, 4, 4.5, 5, 6, 8, 12, 24, 48, 72, and 96 hours post-dose in both periods.
Dolutegravir PK sampling			X	X	D3, D4, D5		X	X	X	X	Blood for PK analysis of dolutegravir will be collected within 40 minutes prior to dosing and 0.5, 1, 1.5, 2, 2.5, 3, 3.5, 4, 4.5, 5, 6, 8, 12, 24, 48, 72, and 96 hours post-dose in both periods.
AE review			←=====X=====→								
SAE review			←=====X=====→								
Concomitant medications			←=====X=====→								

AE = adverse event; D = day; ECG = electrocardiogram; PK = pharmacokinetic; QTcF = QT interval corrected using Fridericia's formula; SAE = serious adverse event.

1 Baseline assessments will be collected on Day -1 before Period 1.

2 Evaluations scheduled for Day 5 in Period 2 will also be performed for participants who discontinue early.

3 Review and approval prior to dosing on Day 1 of Periods 1, 2 and 3.

The timing of planned study assessments may change during the course of the study based on emerging data/in-stream data review (e.g., to obtain data closer to the time of peak plasma concentrations) to ensure appropriate monitoring. Any changes in the timing of time points for any planned study assessments as the result of emerging PK data from this study must be documented and approved by the relevant study team member and then archived in the sponsor and site study files but will not constitute a protocol amendment. The Institutional Review Board (IRB) or Independent Ethics Committee (IEC) will be informed of any safety issues that constitute a substantial amendment and require alteration of the safety monitoring scheme or amendment of the informed consent form (ICF). The changes will be approved by the healthy authority and the ethics committee before implementation.

11.2. Appendix 2: Study Phases and Treatment Emergent Adverse Events

11.2.1. Study Phases

Assessments and events will be classified according to the time of occurrence relative to study treatment start date(/time) and stop date(/time).

Study Phase	Definition
Pre-Treatment	Date and Time \leq Study Treatment Start Date and Time
On-Treatment	Study Treatment Start Date and Time $<$ Date and Time \leq Study Treatment Stop Date and Time + 5 days the Date and Time of Early Withdrawal Visit whichever is later.
Post-Treatment	Date and Time $>$ Study Treatment Stop Date and Time + 5 days or the Date and Time of Early Withdrawal Visit whichever is later

11.2.1.1. Study Phases for Concomitant Medication

Study Phase	Definition
Prior	If medication end date is not missing and is before Day -1
Concomitant	Any medication that is not a prior

NOTES:

- Please refer to Appendix 5: Reporting Standards for Missing Data for handling of missing and partial dates for concomitant medication. Use the rules in this table if concomitant medication date is completely missing.

11.2.2. Treatment Emergent Flag for Adverse Events

Flag	Definition
Treatment Emergent	
 • If AE onset date and time is on or after treatment start date and time & on or before treatment stop date and time + 5 days within each treatment period. • Study Treatment Start Date and Time \leq AE Start Date and Time \leq Study Treatment Stop Date and Time + 5 days within each treatment period. • If the AE onset date is completely missing, the AE is considered as treatment emergent.

NOTES:

- If the study treatment stop date is missing, then the AE will be considered to be On-Treatment.
- Please refer to Appendix 5: Reporting Standards for Missing Data for handling of missing and partial dates for AEs. Use the rules in this table if the AE onset date is completely missing.

11.3. Appendix 3: Data Display Standards & Handling Conventions

11.3.1. Reporting Process

Software	

 The currently supported versions of SAS software (9.4) will be used. 	
Reporting Area	
HARP Server	\lus1salx00259.corpnet2.com
HARP Compound	GSK3640254
Analysis Datasets	

 Analysis datasets will be created according to CDISC standards (SDTM IG Version 3.2 & ADaM IG Version 1.1). For creation of ADaM datasets (ADC1/ADCM/ADAE), the same version of dictionary datasets will be implemented as those being used for conversion from SI to SDTM. 	
Generation of RTF Files	

 RTF files will be generated for all reporting efforts described in the RAP. 	

11.3.2. Reporting Standards

General	

 The current GSK Integrated Data Standards Library (IDSL) will be applied for reporting, unless otherwise stated (IDSL Standards Location: https://spope.gsk.com/sites/IDSLLibrary/SitePages/Home.aspx): 
 4.03 to 4.23: General Principles 5.01 to 5.08: Principles Related to Data Listings 6.01 to 6.11: Principles Related to Summary Tables 7.01 to 7.13: Principles Related to Graphics Do not include participant level listings in the main body of the GSK CSR. All participant level listings should be located in the modular appendices as ICH or non-ICH listings. MedDRA version 24.0 will be applied for reporting, unless otherwise stated. 	
Formats	

 All data will be presented by study part separately. All data will be reported according to the actual treatment the participant received unless otherwise stated. GSK IDSL Statistical Principles (5.03 & 6.06.3) for decimal places (DP's) will be adopted for reporting of data based on the raw data collected, unless otherwise stated. Numeric data will be reported at the precision collected on the eCRF. The reported precision from non eCRF sources will follow the IDSL statistical principles but may be adjusted to a clinically interpretable number of DP's. 	
Planned and Actual Time	

 Reporting for tables, figures, and formal statistical analyses: 
 Planned time relative to dosing will be used in figures, summaries, statistical analyses and calculation of any derived parameters, unless otherwise stated. For procedures without predose assessment within period, the baseline planned time will be the Day 7 of the previous period. The impact of any major deviation from the planned assessment times and/or scheduled visit days on the analyses and interpretation of the results will be assessed as appropriate. 	


 Reporting for Data Listings: 
 Planned and actual time relative to study drug dosing will be shown in listings (Refer to IDSL Statistical Principle 5.05.1). Unscheduled or unplanned readings will be presented within the participant's listings. Visits outside the protocol defined time-windows (i.e. recorded as protocol deviations) will be included in listings but omitted from figures (mean figures only for PK concentrations), summaries, and statistical analyses (excluding statistical analyses of PK parameters). 	
Unscheduled Visits	

 Unscheduled visits will not be included in summary tables except for determining baseline and the worst-case values. Unscheduled visits will not be included in figures. All unscheduled visits will be included in listings. 	
Descriptive Summary Statistics	
Continuous Data	Refer to IDSL Statistical Principle 6.06.1
Categorical Data	N, n, frequency, %
Graphical Displays	

 Refer to IDSL Statistical Principles 7.01 to 7.13. 	

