| Vital signs | | X | X | X | D3 | D7 | X | X | X | X | Blood pressure and pulse will be measured in triplicate at predose on Day 1 in all periods. Single blood pressure and pulse will be measured on other study days. |
| Temperature check | X | X | X | X | X | X | X | X | X | X | |
| 12-lead ECG | | X | X | | | | X | | | X | The ECGs on Day 1 in all periods will be taken at predose, and post-dose at 2, 4, and 6 hours. The predose ECGs will be taken in triplicate to establish a baseline QTcF. The post-dose ECGs are single ECGs. |
| Drug, alcohol, and cotinine screen | X | | | | | | | | | | See Appendix 2 for specific tests to be performed. |

| Procedure | Check-in | Baseline ¹ | Period 1 & 2 | | | Period 3 | | | | Notes | |
|---|----------|-----------------------|--------------|---------|------------|----------|-------|-------|----------|--------------------|--|
| | Day -2 | Day -1 | Day 1 | Washout | | | Day 1 | Day 2 | Days 3-4 | Day 5 ² | |
| | | | | Day 2 | Days 3-5 | Days 6-7 | | | | | |
| Molecular test for SARS-CoV-2 | X* | | | | D5 | | | | | X | * The second test will be performed on Day -2 after admission to the clinic. Participants will be quarantined within the clinic until the second test result is negative. Once the second test result is confirmed negative, participants can be released into the study unit and will follow infection control practices. |
| Laboratory assessments (hematology, chemistry, urinalysis) | | X ³ | | X | | D7 | | X | | X | See Appendix 2 for specific tests to be performed. Day 2 samples in each period to be collected 24 hours after dosing. |
| Pregnancy test | X | | | | | | | | | X | Serum testing on Day -2 |
| Columbia-Suicide Severity Rating Scale | | X | | | | D7 | | | | X | |
| Study intervention: GSK3640254 25 mg, 100 mg or GSK3640254 / DTG 150 mg / 50 mg fixed-dose combination Or DTG 50 mg | | | X | | | | X | | | | See Section 4.1. |
| GSK3640254 PK sampling | | | X | X | D3, D4, D5 | | X | X | X | X | Blood for PK analysis of GSK3640254 will be collected within 40 minutes prior to dosing and 0.5, 1, 1.5, 2, 2.5, 3, 3.5, 4, 4.5, 5, 6, 8, 12, 24, 48, 72, and 96 hours post-dose in all periods. |
| Dolutegravir PK sampling | | | X | X | D3, D4, D5 | | X | X | X | X | Blood for PK analysis of dolutegravir will be collected within 40 minutes prior to dosing and 0.5, 1, 1.5, 2, 2.5, 3, 3.5, 4, 4.5, 5, 6, 8, 12, 24, 48, 72, and 96 hours post-dose in all periods. |

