11.9.5. Safety Tables

Safety: Tables					
No.	Population	IDSL / Example Shell	Title	Programming Notes	Deliverable [Priority]
Adverse Events (AEs)					
2.1.	Safety	AE1xo	Summary of Adverse Events by System Organ Class and Preferred Term – Part 1		SAC
2.2.	Safety	AE1xo	Summary of Adverse Events by System Organ Class and Preferred Term – Part 2		SAC
2.3.	Safety	AE1xo	Summary of Drug-Related Adverse Events by System Organ Class and Preferred Term – Part 1		SAC
2.4.	Safety	AE1xo	Summary of Drug-Related Adverse Events by System Organ Class and Preferred Term – Part 2		SAC
2.5.	Safety	AE3	Summary of Common (>=5%) Adverse Events by Overall Frequency – Part 1		SAC
2.6.	Safety	AE3	Summary of Common (>=5%) Adverse Events by Overall Frequency – Part 2		SAC
2.7.	Safety	AE15	Summary of Common (>=5%) Non-serious Adverse Events by System Organ Class and Preferred Term – Part 1 (Number of Subjects and Occurrences)		SAC

Safety: Tables					
No.	Population	IDSL / Example Shell	Title	Programming Notes	Deliverable [Priority]
2.8.	Safety	AE15	Summary of Common (>=5%) Non-serious Adverse Events by System Organ Class and Preferred Term – Part 2 (Number of Subjects and Occurrences)		SAC
2.9.	Safety	AE16	Summary of Serious Adverse Events by System Organ Class and Preferred Term – Part 1 (Number of Subjects and Occurrences)		SAC
2.10.	Safety	AE16	Summary of Serious Adverse Events by System Organ Class and Preferred Term – Part 2 (Number of Subjects and Occurrences)		SAC
2.11.	Safety	AE5A	Summary of Adverse Events by System Organ Class and Preferred Term and Maximum Intensity – Part 1		SAC
2.12.	Safety	AE5A	Summary of Adverse Events by System Organ Class and Preferred Term and Maximum Intensity – Part 2		SAC
2.13.	Safety	AE1xo	Summary of Adverse Events of Special Interest by System Organ Class and Preferred Term – Part 1		SAC
2.14.	Safety	AE1xo	Summary of Adverse Events of Special Interest by System Organ Class and Preferred Term – Part 2		SAC
Laboratory: Chemistry					
2.15.	Safety	LB1	Summary of Clinical Chemistry Data – Part 1		SAC
2.16.	Safety	LB1	Summary of Clinical Chemistry Data – Part 2		SAC
2.17.	Safety	LB1	Summary of Clinical Chemistry Changes from Baseline – Part 1		SAC
2.18.	Safety	LB1	Summary of Clinical Chemistry Changes from Baseline – Part 2		SAC
2.19.	Safety	LB16	Summary of Clinical Chemistry Results by Maximum Grade Increase Post-Baseline Relative to Baseline – Part 1		SAC

Safety: Tables					

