No.	Population	IDSL / Example Shell	Title	Programming Notes	Deliverable [Priority]
2.20.	Safety	LB16	Summary of Clinical Chemistry Results by Maximum Grade Increase Post-Baseline Relative to Baseline – Part 2		SAC
Laboratory: Hematology					
2.21.	Safety	LB1	Summary of Hematology Data – Part 1		SAC
2.22.	Safety	LB1	Summary of Hematology Data – Part 2		SAC
2.23.	Safety	LB1	Summary of Hematology Changes from Baseline – Part 1		SAC
2.24.	Safety	LB1	Summary of Hematology Changes from Baseline – Part 2		SAC
2.25.	Safety	LB16	Summary of Hematology Results by Maximum Grade Increase Post-Baseline Relative to Baseline – Part 1		SAC
2.26.	Safety	LB16	Summary of Hematology Results by Maximum Grade Increase Post-Baseline Relative to Baseline – Part 2		SAC
Laboratory: Urinalysis					
2.27.	Safety	LB1	Summary of Urine Concentration – Part 1		SAC
2.28.	Safety	LB1	Summary of Urine Concentration – Part 2		SAC
2.29.	Safety	LB1	Summary of Urine Concentration Changes from Baseline – Part 1		SAC
2.30.	Safety	LB1	Summary of Urine Concentration Changes from Baseline – Part 2		SAC
2.31.	Safety	UR3	Summary of Urinalysis Dipstick Results – Part 1		SAC
2.32.	Safety	UR3	Summary of Urinalysis Dipstick Results – Part 2		SAC
2.33.	Safety	LB16	Summary of Urinalysis by Maximum Grade Increase Post-Baseline Relative to Baseline – Part 1		SAC
2.34.	Safety	LB16	Summary of Urinalysis by Maximum Grade Increase Post-Baseline Relative to Baseline – Part 2		SAC

Safety: Tables					
No.	Population	IDSL / Example Shell	Title	Programming Notes	Deliverable [Priority]
ECG					
2.35.	Safety	SAFE_T1	Summary of ECG Findings – Part 1		SAC
2.36.	Safety	SAFE_T1	Summary of ECG Findings – Part 2		SAC
2.37.	Safety	EG2	Summary of ECG Values – Part 1		SAC
2.38.	Safety	EG2	Summary of ECG Values – Part 2		SAC
2.39.	Safety	EG2	Summary of ECG Changes from Baseline – Part 1		SAC
2.40.	Safety	EG2	Summary of ECG Changes from Baseline – Part 2		SAC
2.41.	Safety	EG10	Summary of Maximum QTc Values Post-Baseline Relative to Baseline by Category – Part 1		SAC
2.42.	Safety	EG10	Summary of Maximum QTc Values Post-Baseline Relative to Baseline by Category – Part 2		SAC
2.43.	Safety	EG11	Summary of Maximum Increase in QTc Values Post-Baseline Relative to Baseline by Category – Part 1		SAC
2.44.	Safety	EG11	Summary of Maximum Increase in QTc Values Post-Baseline Relative to Baseline by Category – Part 2		SAC
Vital Signs					
2.45.	Safety	VS1	Summary of Vital Signs – Part 1		SAC

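### As written, SAP 11.3.2 bars scheduled safety readings logged as out of window from the maximum-QTc and maximum-grade tables, although unscheduled readings count there

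*SAP*

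**What the plan says.** Two adjacent blocks of SAP 11.3.2 treat irregular readings differently.

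- **Out of window.** "Visits outside the protocol defined time-windows (i.e. recorded as protocol deviations) will be included in listings but omitted from figures". The same sentence carries the omission on to further outputs ("summaries, and statistical analyses (excluding statistical analyses of PK parameters"). Its two exceptions both concern PK: for concentrations only the mean figures are affected, and the PK-parameter analyses are exempt. Safety data have no exception.
- **Unscheduled.** "Unscheduled visits will not be included in summary tables except for determining baseline and the worst-case values".

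SAP 11.9.5 lists tables built on a participant's worst value. Table 2.41 is "Summary of Maximum QTc Values Post-Baseline Relative to Baseline by Category – Part 1" and Table 2.43 is "Summary of Maximum Increase in QTc Values Post-Baseline Relative to Baseline by Category – Part 1"; 2.42 and 2.44 are the Part 2 versions. For laboratory grade, Table 2.19 is "Summary of Clinical Chemistry Results by Maximum Grade Increase Post-Baseline Relative to Baseline – Part 1" and Table 2.25 is "Summary of Hematology Results by Maximum Grade Increase Post-Baseline Relative to Baseline – Part 1". Tables 2.20 and 2.26 are their Part 2 versions, and 2.33–2.34 do the same for urinalysis.

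The readings behind the QTc tables are few. Protocol 1.3 says: "The ECGs on Day 1 in all periods will be taken at predose, and post-dose at 2, 4, and 6 hours". The post-dose tracings are single, and no tolerance is given around those hours.

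**The concern.** An unplanned reading may set a participant's maximum, but a planned reading logged as mistimed may not. The SAP gives no reason for the difference. Timing accuracy matters for a mean at 2, 4 or 6 hours. It matters much less for the question of how high a value went after dosing.

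QT prolongation is a named risk of GSK3640254 (Protocol 2.3 and 2.3.1), and observed values and changes in ECG and laboratory tests are secondary endpoints (Protocol 3). SAP 11.3.2 also keeps participant-level listings out of the main body of the study report. If a high reading is excluded, the table in the body understates that participant's maximum and the correct value appears only in an appendix.

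**Working it through.** No figure in the plan needs reproducing. The check sets the rules side by side and then follows a reading through them.

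**1. Treatment of each kind of safety reading**

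| Reading | By-time-point summaries | Baseline | Maximum / worst case | Listings |
|---|---|---|---|---|
| Scheduled, in window | used | used | used | yes |
| Unscheduled | not used | used | used | yes |
| Scheduled, logged out of window | not used | no exception in 11.3.2, but SAP 5.2 sets no window condition | not used (no exception) | yes |

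**2. Is there an override?** SAP 8.2, 8.4, 11.4.1 and 11.5 contain nothing that restores an out-of-window value for worst case. SAP 5.2 deals only with baseline. SAP 11.3.2 promises to assess the impact of major timing deviations where appropriate, but that is not a derivation rule.

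**3. Direction.** Let S be all post-baseline readings and S′ those left after omission. Then max(S′) ≤ max(S). With baseline B unchanged, max(S′) − B ≤ max(S) − B. The tabulated maximum and maximum increase can stay the same or fall, and cannot rise.

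**4. Which QTcF values are exposed.** The inputs are the potential-clinical-importance limit of >450 msec (SAP 11.7.1) and the repeat-ECG trigger of >500 msec or an increase >60 msec (Protocol 7.1.2).

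- *451–500 msec, increase 60 msec or less:* above the SAP limit and below the trigger, so no repeat is required. If this is the participant's only reading above 450 msec and it is logged as out of window, the tabulated maximum falls to 450 msec or below.
- *Above 500 msec, or increase above 60 msec:* two unscheduled repeats are required within 10 minutes, and these count for worst case. In an invented example, changes of 12, 64 and 18 msec at 2, 4 and 6 hours, with the 4-hour reading out of window, give a maximum of 18 instead of 64 from scheduled readings alone. The repeats restore a value above 60 if they reproduce it.

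**5. Laboratory values.** Protocol 8.2.4 requires values judged clinically significantly abnormal to be repeated. Those unscheduled repeats count, but a repeat may carry a lower grade than the omitted value. A graded value not judged clinically significant need not be repeated at all.

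**6. Scale (illustration only).** The documents give no out-of-window rate. I assume 1–5%, unrelated to the value read. With about 18 participants per part (SAP 2.5), Day 1 post-dose ECGs number:

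- Part 1: 18 × 3 periods × 3 = 162
- Part 2: 18 × 2 periods × 3 = 108

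Later ECGs, such as the Day 5 discharge tracing, are left out of this count. Readings omitted: 162 × 0.01 to 0.05 = 1.6 to 8.1, and 108 × 0.01 to 0.05 = 1.1 to 5.4. A maximum changes only if the omitted reading was the highest. Taking that as one in three, the maxima affected are 0.5 to 2.7 and 0.4 to 1.8.

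The chance that at least one participant's maximum is lost in a given treatment is 1 − (1 − f)ⁿ, where f is the assumed share of participants whose maximum falls on an omitted reading:

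| n | f = 1% | f = 5% |
|---|---|---|
| 18 | 1 − 0.99¹⁸ = 16.5% | 1 − 0.95¹⁸ = 60.3% |
| 14 | 1 − 0.99¹⁴ = 13.1% | 1 − 0.95¹⁴ = 51.2% |

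These count maxima of any size. Only some would cross a QTc category, and the documents do not show the category limits. One participant is 5.6% of 18 or 7.1% of 14.

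**The case against.** The other side has a good deal to say.

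- **The rule may rarely apply.** It covers visits outside protocol windows that are recorded as deviations. The protocol states no tolerance for post-dose ECGs or laboratory tests, and participants are confined throughout. The word visits might also mean whole visits and not time points. This stands: the reach is small and depends on what is logged. It does not settle how a logged reading should be treated.
- **Large excursions are caught.** A reader might infer that a QTcF above 500 msec could vanish from the tables. The documents do not support that in general, because Protocol 7.1.2 requires repeats that count. Only an excursion that the repeats fail to reproduce is lost.
- **Nothing leaves the report.** All ECG values are in Listings 63–64 and graded laboratory values in Listings 47–58. Clinically significant findings are recorded as AEs (Protocol 2.3.1 and 8.2.4). This stands, and it limits the harm to the summary tables.
- **Baseline is probably safe.** A reader might infer that a mistimed Day 7 laboratory sample is lost as the next period's baseline. SAP 5.2 takes the most recent non-missing pre-dose result, with no window condition, so this is unlikely. It also matters for direction: if a high baseline were dropped, a change from baseline could rise. The argument that omission only lowers results therefore applies to post-baseline maxima alone.
- **Sponsor display standards may cover it.** SAP 11.3.2 invokes the sponsor's standards library, which is not reproduced. Those standards apply unless the SAP states otherwise, and on out-of-window visits it states its own rule.

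**Conclusion.** The concern holds in a limited form and is minor. Read literally, the SAP lets an unscheduled reading set a participant's maximum and bars a scheduled reading logged as out of window from doing so. The effect on Tables 2.41–2.44, 2.19–2.20, 2.25–2.26 and 2.33–2.34 is one-sided, towards lower maxima. The cases with least protection are a QTcF of 451–500 msec with an increase of 60 msec or less, and a graded laboratory value not reproduced on repeat.

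A reader might infer that every safety summary is affected. That goes too far: AE and AESI tables assign events by onset relative to dosing (SAP 8.1 and 11.2.2), so a visit-window rule does not govern them. Safety is also descriptive, with no formal analysis (Protocol 9.4.2), so no inference is distorted.

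The conclusion assumes that the rule applies to individual time points and that some safety readings will be logged as out of window. How often that will happen cannot be derived from the documents, and the 1–5% range is an assumption.

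**What to change.** Add one clause to SAP 11.3.2. Safety assessments outside their window are omitted only from by-time-point summaries and figures. Like unscheduled values, they are used for maximum post-baseline QTc, maximum laboratory grade and other worst-case tables, and for baseline where they meet SAP 5.2.

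In the same edit, say where the windows for ECGs and laboratory tests are defined, so that a reading's status does not depend on case-by-case logging. Settle both points before unblinding, alongside the deviation review in SAP 4.1.

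The cost is one clause and a small change to the derivation of the worst-case records. No new data are needed, the schedule of assessments does not change, and by-time-point summaries and PK analyses stay as planned.
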